- *Locator Form.* This form is used during the Attendance Phase to collect information that assists research staff in tracking clients for follow-up interviews. The form asks for such information as date of birth, Social Security number, driver's license, vehicle license number, locations of hangouts, and addresses and phone numbers of family and friends (see further details below under *Tracking and Locating*). During the Admission Phase only a brief locator form is used. The brief locator form is used to collect an address to send the Admission Phase gift card. This form is also used to record the client's expected parole date so that research staff will know when to start tracking the client's admission (or not) to Walden House.

During both the Admission and Attendance phases, a brief description of that phase's incentive program and its philosophy is provided after completion of the informed consent form and locator form, but before the structured baseline interviews. The goals are to -

- Orient applicants to what will happen in treatment.
- Create an atmosphere of optimism about treatment outcome.
- Make applicants feel hopeful about improving their life situation.
- The intake worker should also explain that –
 - The program is confidential; everything discussed or written remains private.
 - Each person who signs up to be in the study has a 50/50 chance of gaining entry into the incentives group for admission, and another 50/50 chance of gaining entry into the attendance incentives group following entry into the Walden House program. Only half of the people in the study will receive vouchers.
 - The Attendance intervention lasts for up to 22 weeks.
 - The client will begin earning incentives (only if he is in the incentive group) beginning on the Monday following his entry into the Attendance phase of the study
- The intake worker also provides a very brief description of the voucher incentive program.

If you are randomly selected to participate in the information group, you will attend a half-hour session on why it is helpful to stay in treatment, receive a brochure with that same information and receive a Target gift card for \$20.

If you are randomly selected to participate in the incentives program:

“When you attend treatment, you will earn vouchers. These vouchers indicate the amount of money you earn for treatment participation. You can accumulate

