to locate subjects for follow-up is that supplied by subjects at the baseline interview, which includes the individual's driver's license, vehicle license, and Social Security numbers; names, addresses, and phone numbers of immediate relatives and of two unrelated friends; date and place of birth; areas of town the subject frequents (particularly if he has a history of homelessness); and locations where social services are received (if relevant). Other useful tracking sources are agency records (Department of Corrections, Department of Motor Vehicles, Social Security Administration, local jails). When participants are recruited into the Attendance Phase, the interviewer will update the locator information. These procedures are described in a manual developed at ISAP ([name] et al., 2003; see Appendix D). All randomized subjects, except those who have requested that they be dropped from the study, will be tracked for the 12-month follow-up interview. Since detailed locator information will be available, and since nearly all of the subjects at the time of the follow-up assessment will still be under correctional supervision, we expect to locate and interview at least 85% of the baseline sample. ISAP has demonstrated its ability to track and locate subjects for as long as 10 years between interview points, with location rates of 90% or greater in most studies (Hser, Anglin, & Powers, 1993). In its longest follow-up study to date, a 33-year follow-up of a cohort (n=581) that entered treatment in 1962-1963, 40% were interviewed, 6% were located but not interviewed (includes refusals, severely impaired, contacted but not interviewed), 49% were confirmed to have died, and 6% were not located (Hser, Hoffman, Grella, & Anglin, 2001). In a recent multi-site study of case management with parolees, the follow-up rates for the ISAP study site were 93 % at three months and 89% at nine months.

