For the primary outcomes of admission and attendance, there will be no attrition since these outcomes will be based on program records. For the Admission Phase, the target sample size of 250 will allow detection of medium effects in comparisons between groups on the percentage of clients who enroll in treatment at Walden House, with $\alpha = .05$ (two-tailed) and power .80. For the Attendance Phase, with retention as the outcome, the sample size of 200 will allow detection of similar effects between groups. For the 12-month outcomes, the effect size will be smaller, possibly around $d = 0.30$, based on a previous meta-analysis of drug abuse treatment generally (Prendergast, Podus, Chang, & Urada, 2002). Here, where the analysis will be based on the follow-up interview sample in the Attendance Phase (~170), power is likely to be about .75. For arrest and reincarceration, where there will be no attrition, power will be at least .80. Inclusion of covariates may increase power somewhat (Tabachnick & Fidell, 1996).

PRELIMINARY AND DESCRIPTIVE ANALYSES

As noted above, faxable forms will allow many of the instruments to be quickly entered and checked, making it possible to periodically examine the data. Descriptive statistics on variables of interest will include percentages, means, correlations, measures of variance, and distribution characteristics, as appropriate to the measurement level of selected variables. Frequency tables will be used to examine cell sizes for categorical variables and non-normality for continuous variables. Where categorical variables have small cell sizes, we will collapse the categories where possible to create cells of sufficient size. Where variables are non-normally distributed, we will transform the variable if possible or use a non-parametric approach. If outliers are present, they may be recoded or omitted. Descriptive analyses will provide statistics on treatment-related variables, including percentage of sessions attended, number of weeks attended, value of vouchers earned, and items for which vouchers were redeemed.

DESIGN ANALYSES

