Hypothesis tests are based on the assumption of group equivalence due to random assignment. However, if preliminary analysis indicates significant baseline differences, then additional control variables will be included in the analyses. Hypotheses will be tested using a two-sided .05 level of significance.

Hypotheses will initially be tested using t-tests and chi-square tests. T-tests will be used to conduct pairwise comparisons of participants in the study groups on outcomes measured as a single continuous variable. For categorical and binary outcome variables, we will use chi-square analysis. If covariates are required, analyses will be extended to ordinary least squares (OLS) or logistic regression as appropriate to the scale properties of the dependent variable. Because of missing data, inclusion of covariates, and/or repeated measures for binary outcomes, analyses may be extended to generalized linear models (McCullagh & Nelder, 1989). Structural equation modeling will be used to determine whether the effect of incentives on distal outcomes is mediated by program admission, treatment activities, admission, or retention (Kaplan, 2000).

For each hypothesis, an effect size will be calculated. The index of effect size will be the standardized mean difference (calculated as the difference between two groups divided by the pooled standard deviation); for proportions, the equivalent effect size is calculated using the arc sine transformation (Lipsey & Wilson, 2001). An effect size for study outcomes will provide a

quantitative indication of the magnitude of the difference between groups; it will also be useful in calculating power for any future study of this intervention.

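### Power for the 12-month outcomes is stated as .75 and at least .80, but the protocol's own effect size, sample sizes and alpha give about .50 and .56

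*Protocol*

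**What the plan says.** The Power Analysis section first sizes the study for its two primary aims. For the second of these it states: "For the Attendance Phase, with retention as the outcome, the sample size of 200 will allow detection of similar effects between groups".

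It then turns to the long-term outcomes and lowers the expected effect: "For the 12-month outcomes, the effect size will be smaller, possibly around $d = 0.30", citing a meta-analysis of drug abuse treatment in general. For these outcomes "the analysis will be based on the follow-up interview sample in the Attendance Phase (~170"), and the resulting claim is that "power is likely to be about .75. For arrest and reincarceration, where there will be no attrition, power will be at least .80". Covariates are mentioned afterwards, as a possible further gain.

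The other inputs are elsewhere in the protocol:

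- Hypothesis Testing: "Hypotheses will be tested using a two-sided .05 level of significance".
- Tracking and Locating: "we expect to locate and interview at least 85% of the baseline sample". This explains the 170, since 0.85 × 200 = 170.
- Recruitment - Intake Procedures: participants are told they have "another 50/50 chance of gaining entry into the attendance incentives group following entry into the Walden House program", so allocation is 1:1.

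**The concern.** The paragraph gives an effect size, a sample size, a significance level and a power, and any three of these determine the fourth. A difference of 0.30 standard deviations with 85 per arm is well known to give power far short of .75. Moving from 170 to 200 participants, which is the only reason offered for the higher figure on arrest and reincarceration, cannot add enough to reach .80.

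At stake is how Aims 4 and 5 are read. H5 to H9 cover abstinence, arrest and reincarceration, psychosocial functioning, HIV-risk behaviour and HIV-related services, each tested at .05. A reader told that power is .75 to .80 or more would reasonably treat a non-significant result as fair evidence against a lasting benefit. If true power is near .50, that inference is not supported.

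**Working it through.** **Inputs.** d = 0.30; N = 170 for interview outcomes and N = 200 for records outcomes (Power Analysis); 1:1 allocation (Recruitment - Intake Procedures); two-sided alpha .05, so z = 1.960 (Hypothesis Testing). The planned tests are t-tests and chi-square tests.

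**Formula.** For two equal groups with N in total, power ≈ Φ(d × √(N/4) − 1.960).

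**Trying to reproduce the stated figures.**

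- N = 170: 0.30 × √42.5 = 1.956; 1.956 − 1.960 = −0.004; Φ = **.498**. The noncentral t gives .494. Stated: about .75.
- N = 200: 0.30 × √50 = 2.121; 2.121 − 1.960 = 0.161; Φ = **.564**. The noncentral t gives .560. Stated: at least .80.

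Neither figure is reproduced.

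**Binary outcomes.** Hypothesis Testing treats the arcsine effect size for proportions as equivalent to d. With h = 0.30 and one group's rate between 20% and 70%, power is .49 to .50 at N = 170 and .55 to .56 at N = 200. The scale of the outcome does not explain the gap.

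**Other readings, all at d = 0.30 (normal approximation).**

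| Reading | Interview outcomes | Records outcomes |
|---|---|---|
| As written | .50 | .56 |
| One-sided .05 | .62 | .68 |
| 170 and 200 per arm | .79 | .85 |
| All 250 Admission Phase participants, two-sided | not applicable | .66 |

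The one-sided reading contradicts Hypothesis Testing. The per-arm reading contradicts the stated Attendance Phase total of 200 and overshoots .75. The 250 are the wrong population, because H5 to H9 compare the Attendance groups. Unequal allocation only lowers power (at 2:1, .45 for N = 170).

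**Covariates.** For a continuous outcome in a linear model, adjustment would have to raise the effective d to the value that gives the stated power: 0.404 for .75 at N = 170, and 0.396 for .80 at N = 200. The variance to be explained is 1 − (0.30/0.404)² ≈ .45 and 1 − (0.30/0.396)² ≈ .43. The protocol expects only a modest gain from covariates. This calculation does not carry over directly to the binary outcomes.

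**What does fit.** With d = 0.40:

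- N = 170: 0.40 × √42.5 − 1.960 = 0.648, power .74.
- N = 200: 0.40 × √50 − 1.960 = 0.868, power .81.

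Both stated figures match an effect of about 0.40, a third larger than the one assumed.

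**What d = 0.30 would need.** N = 4 × (1.960 + z)² / 0.30². For power .75 (z = 0.674) this is about 310 analysed; for .80 (z = 0.842) it is about 350.

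**Detectable effect at 80% power.** d = (1.960 + 0.842) × √(4/N): 0.43 at N = 170 and 0.40 at N = 200.

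**The case against.** The strongest reply is that the documents show only that d, N and power do not fit together, not which one is wrong. Since 0.40 reproduces both power figures, the 0.30 may be the slip. That is a fair account of how the error may have arisen. But 0.30 is the only effect size the protocol gives for these outcomes, it is argued for there, and the text expressly makes it smaller than the effects expected during treatment. As written, the power figures do not follow.

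Second, no separate effect size is given for arrest and reincarceration, and Hypothesis Testing counts these events over 18 months from release, including the intervention period. The .56 is therefore conditional on carrying 0.30 across. That is the natural reading, because H6 places these among the Month 12 outcomes and the only advantage claimed for them is the absence of attrition.

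Third, these are secondary outcomes; the protocol says it is powered for admission and attendance, and effect sizes are already promised for every hypothesis. This is correct and limits the damage: the primary sample size stands, and no relabelling of H5 to H9 is needed. It does not make the figures right.

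Finally, the wording is hedged. Hedging can cover rounding, not 25 points, and "For arrest and reincarceration, where there will be no attrition, power will be at least .80" is stated as a floor. It is true, however, that the protocol nowhere says a null result will be read as no effect; the risk of misreading is an inference from the overstated power.

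**Conclusion.** The point holds. At the protocol's own d = 0.30, two-sided .05 and 1:1 allocation, power is about .50 for the interview outcomes (stated: about .75) and about .56 for arrest and reincarceration (stated: at least .80). The overstatement is about 25 points and at least 24 points. If the assumed effect is real, a non-significant result would occur about half the time on each interview outcome and about 44% of the time on each records outcome.

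This rests on exactly 170 and 200 analysed, equal arms, and 0.30 applying to the records outcomes as well. Small departures from the first two make little difference. The error is confined to the long-term hypotheses and does not touch the sample size for the primary aims.

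**What to change.** Replace the two power figures in the Power Analysis section with text along these lines:

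> At d = 0.30 and a two-sided .05 level, power is about .50 with 170 participants interviewed and about .56 with 200 in the records data. The effects detectable with 80% power are d = 0.43 and d = 0.40 respectively. Results for H5 to H9 will be reported as effect sizes with 95% confidence intervals, and a non-significant result will not be interpreted as absence of an effect.

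If the investigators in fact meant an effect of about 0.40, for either set of outcomes, the section should say so and justify it in place of 0.30.

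The cost is one paragraph of wording and less favourable figures. Enrolment, randomisation, endpoints and planned tests are unchanged, and effect sizes are already to be calculated; only the confidence intervals and the statement on interpretation are new.

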- 7) interviewers administer the appropriate research documentation forms (see Assessment – Research Documentation Forms section)
- 8) interviewers look for reporting inconsistencies and socially desirable responses; and
- 9) consistency checks on reporting are built in as part of the interview process.

The Project Director will periodically sit in on interviews to ensure compliance with interview protocols and to identify problems that need correction. As a quality check, the Project Director will randomly call 10% of participants for whom interview forms are on file to verify that the interview took place and to ask about suggestions on interview procedures (see ISAP's data integrity policy in Appendix C).

RANDOMIZATION

In the Admission Phase, clients will be randomized to the Admission Incentive group or to the Admission Information group. Thus, each client has a 50/50 chance of gaining entry to the Incentive group or the Information group. Those clients in the Admission Phase who show up at Walden House and complete intake process will be consented and re-randomized to the Attendance Incentive group or to the Attendance Information group. In both cases, clients will

be randomly assigned to one of the study conditions using the Urn Randomization Program (version 1.10, developed at Yale University for Clinical Trials Network studies). Urn randomization is a procedure to maintain balance and minimization of bias across study groups for selected characteristics expected to be related to outcome (Stout, Wirtz, Carbonari, & Del Boca, 1994). The following baseline variables that are strongly associated with drug use and/or crime outcomes will be used in urn randomization:

- Race/ethnicity (African American vs. White/Hispanic/Other)
- Risk for recidivism (using the score on the Lifestyle Criminality Screening Form: 0-7 vs. 8-20)
- Parole status (In-Custody Drug Treatment Program vs. voluntary SAP graduate) – because custody arrangements differ between the two groups. In-Custody Drug Treatment Program (ICDTP) clients are considered to be in-custody and cannot leave the program premises without a staff member, while voluntary SAP graduates are not required to stay in the program.

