On a related issue, sample attrition due to participants dropping out of the study or inability to locate participants for follow-up interviews may result in biased estimation of intervention effects. Every effort will be made to retain all participants through the intervention and to interview all participants at follow-up. The tracking and locating procedures described above should minimize attrition. Note that since treatment and criminal justice records data will be available for virtually all study participants, attrition should not be a problem for enrollment, attendance, rearrest, or reincarceration. To check on attrition, we will examine the following questions regarding study dropouts (Hansen et al., 1985): (1) Do dropouts differ from non-dropouts on baseline measures of key demographic variables and dependent variables? (2) Do the rates of attrition differ across the study groups? (3) Do the baseline scores for dropouts differ across the study groups? Although some attrition is expected, the main issue is whether those with data for hypothesis testing differ between study groups on variables that may bias treatment effect estimates or that may limit generalizability of those estimates. If correlates of loss to follow-up are non-systematic across groups, we can be reasonably certain that the outcomes are not biased due to differential attrition. Although aggressive follow-up of clients can limit this problem, during analysis we will check on possible bias by examining arrests and incarcerations from criminal justice records, which will be available for virtually all study participants. Additionally, using baseline characteristics, selection bias models (e.g., Heckman two-step models) may be used to assess the sensitivity of key results to the possibility of such bias (Heckman, 1979).

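### Finding no systematic difference in the dropout checks cannot make the team reasonably certain that the 12-month interview outcomes are free of attrition bias

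*Protocol*

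**What the plan says.** The attrition text is in the Protocol under Design Analyses. It asks whether dropouts differ from non-dropouts at baseline (check 1), whether attrition rates differ by group (check 2), and "Do the baseline scores for dropouts differ across the study groups" (check 3). If the correlates of loss turn out not to be systematic across groups, the stated inference is that "we can be reasonably certain that the outcomes are not biased due to differential attrition". No margin, interval, test level or power is given for judging this.

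The same section has three further safeguards:
- Arrests and incarcerations from official records, available for nearly everyone, will be examined for signs of bias.
- Heckman-type selection models are allowed but not required.
- Missing data are to be handled by maximum likelihood or multiple imputation, or alternatively by methods that tolerate missing values.

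On the amount of loss, Tracking and Locating says "we expect to locate and interview at least 85% of the baseline sample". Power Analysis bases the 12-month interview analysis on about 170 of the 200 Attendance Phase participants.

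**The concern.** The sentence treats failure to find a difference as evidence that there is none. That could be reasonable if the comparisons were precise, but about 30 people split over two arms give very little precision.

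There is also a limit that a larger sample would not remove. Checks 1 and 3 look at baseline measures, and check 2 looks only at how many were lost. None can show whether loss depended on relapse or on leaving treatment, which are things the incentive is meant to change.

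The outcomes at stake come from the follow-up interview: abstinence (H5, with urine testing where done), psychosocial outcomes (H7), HIV-risk behavior (H8) and use of HIV services (H9). A reassuring set of checks could lead these results to be reported as protected against attrition bias when the data cannot show that.

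**Working it through.** **Inputs**
- Attendance Phase sample of 200 (Power Analysis: "the sample size of 200 will allow detection of similar effects between groups").
- Follow-up of at least 85% (Tracking and Locating).
- Equal allocation (Randomization: "each client has a 50/50 chance of gaining entry to the Incentive group or the Information group"), so 100 per arm.
- Expected 12-month effect of about d = 0.30 (Power Analysis).
- Level of .05, two-sided. The Protocol sets this for hypotheses ("Hypotheses will be tested using a two-sided .05 level of significance"); applying it to the dropout checks is an assumption.
- A difference of 0.5 SD. This is an assumption; other values are shown.

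**Number lost.** 200 × 0.85 = 170, which reproduces the Protocol's figure. 200 − 170 = 30 lost, or 15 per arm if losses are equal.

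**Check 3, dropouts by arm, 15 vs 15.** Noncentrality = d × √(n₁n₂/(n₁+n₂)) = 0.5 × √(225/30) = 1.37 on 28 degrees of freedom. Power is 0.262, so a 0.5 SD difference is missed 74% of the time (a 200,000-run simulation gives 73.8%).

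| Setting | Power | Missed |
|---|---|---|
| 15 vs 15, d = 0.3 | 12% | 88% |
| 15 vs 15, d = 0.5 | 26% | 74% |
| 15 vs 15, d = 0.8 | 56% | 44% |
| 15 vs 15, d = 1.0 | 75% | 25% |
| 12 vs 18, d = 0.5 | 25% | 75% |
| 10 vs 20, d = 0.5 | 24% | 76% |

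Power of 80% needs d of about 1.06.

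**Precision of check 3, with no assumed difference.** Half-width of the 95% interval = t(0.975, 28) × √(2/15) = 2.048 × 0.365 = 0.75 SD. An observed difference of exactly zero is therefore compatible with about −0.75 to +0.75 SD.

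**Check 2, attrition rates, 100 per arm.** With 15% lost in each arm, the half-width is 1.96 × √(2 × 0.15 × 0.85/100) = 1.96 × 0.0505 = 0.099, about 10 percentage points. Power for 10% vs 20% attrition is about 51%.

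**Check 1, dropouts vs non-dropouts, 30 vs 170.** Noncentrality = 0.5 × √(30 × 170/200) = 2.52. Power is 71%, so 29% are missed.

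**Possible bias in the completer estimate.** Let E_c be the arm effect among completers and E_d the effect among dropouts, with 15% lost in each arm. The whole-sample effect is 0.85·E_c + 0.15·E_d, so the bias is E_c − (0.85·E_c + 0.15·E_d) = 0.15 × (E_c − E_d). If the two effects differ by 0.5 SD, the bias is 0.15 × 0.5 = 0.075 SD, and 0.075/0.30 = one quarter of the expected effect.

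**The case against.** The best defense is that the sentence is conditional and hedged, and that no analysis depends on it. Maximum likelihood or multiple imputation is planned whatever the checks show. The records check is a firm commitment and uses post-randomization data on interviewed and lost participants alike. Admission, retention, rearrest and reincarceration come from records and are untouched. Imputation details normally belong in a SAP, which is not available here. All of this stands, and it limits the point to one inference about secondary outcomes.

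It does not rescue the inference. The Protocol does not say how a difference in arrests or incarcerations would alter the analysis of H5 or H7-H9. The selection model is optional, and standard imputation assumes that loss is explained by the observed data.

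Several stronger readings are tempting but unsupported:
- **All the checks miss 0.5 SD 74% of the time.** That figure is for check 3 only. Check 1 misses 29%, and check 2 has no SD scale.
- **The plan would nearly always declare the outcomes unbiased.** The text is conditional, sets no significance rule for the checks, and no joint probability of passing all three has been computed.
- **All the attrition scrutiny is at baseline.** Check 2 and the records check are not baseline data.
- **Custody removes the interview.** Follow-up Interview Procedures provides for interviews in jail or prison. Custody removes the urine test, which touches part of H5.
- **A 0.5 SD gap between the two dropout groups shifts the result by 0.075 SD.** What matters is the contrast with completers. With a whole-sample effect of 0.30, a dropout effect of +0.5 gives completers (0.30 − 0.075)/0.85 = 0.265, a bias of −0.035. A dropout effect of −0.5 gives (0.30 + 0.075)/0.85 = 0.441, a bias of +0.141.

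**Conclusion.** The concern holds in a limited form. A null result in the dropout checks is weak evidence at this size and cannot support reasonable certainty that differential attrition caused no bias. The between-arm comparison of dropouts has 26% power at 0.5 SD, and its interval is about ±0.75 SD even when the observed difference is zero. The interval result needs no assumed effect and no significance rule, only about 15 lost per arm. Because 85% follow-up is a stated minimum, actual loss may be smaller; that would reduce the possible bias but make check 3 weaker still.

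The 0.075 SD bias illustrates what could go unnoticed and is not a prediction. It assumes 15% loss in each arm and an arm effect that differs by 0.5 SD between completers and dropouts. The reach is the secondary interview outcomes, H5 and H7-H9; the primary outcomes are not in question.

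**What to change.** 1. Delete the sentence that draws reasonable certainty from the dropout checks.
2. Report attrition by arm, and the dropout differences, as estimates with 95% confidence intervals.
3. For H5 and H7-H9, use multiple imputation (already among the planned options) with arm, baseline values, days in treatment, and arrest and reincarceration records in the model. This also ties the records check to the outcomes it is meant to protect.
4. Commit to one sensitivity analysis for loss that depends on unobserved outcomes, such as a delta shift, and run it whatever the checks show.

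Items 3 and 4 can be placed in the SAP. The cost is a wording change and modest extra analysis of data already being collected. The price is more cautious conclusions, and probably somewhat wider intervals, for the secondary interview outcomes.
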